9.3.2. Procedures for Early Withdrawal

If a patient withdraws or is removed from the study for any reason prior to Week 78, all EOT procedures should be completed. In addition, the patient should return 4 weeks after last dose of IMP for the Week 82/EOS procedures. Reason for withdrawal, date of the discontinuation, and date of the last dose of study drug should be recorded in the appropriate section of the eCRF. Additionally, the discontinuation visit date must be registered in IWRS. Study drug assigned to the withdrawn patient may not be assigned to another patient.

All effort should be made to have each patient complete all study visits on schedule according to the protocol. Accommodations for early or late visits in special circumstances will be considered by the Sponsor to prevent early withdrawal. Written notice (regardless of cause) is to be provided within 48 hours of the withdrawal to the Sponsor personnel or the Medical Monitor. At the time of discontinuation, every effort should be made to ensure all relevant procedures and evaluations scheduled for the final study visit are performed. Except in the case of a medical emergency, the procedures and assessments detailed in Section 9.2.6 will be performed upon the discontinuation of the study.

Patients choosing to withdraw from the study early should be encouraged to return for all study scheduled clinic visit even if they are no longer taking IMP. Patients who withdraw from all aspects of the study will be asked to consent to clinical visits or phone calls for safety assessments, including AEs, concomitant medication, and current health status through Month 19 (Week 82).

10. ASSESSMENT OF SAFETY

10.1. Safety Parameters

At all clinic visits, investigators will review all safety information including vital signs, AEs, and concomitant medications and will ensure that the collected data are recorded into the appropriate eCRF. Additionally, clinical laboratory samples will be collected and sent for analysis and the investigator will review the results to ensure continued patient safety while participating in the study.

10.1.1. Demographic/Medical History

Demographic and medical history collected from the parent study will be used for this study. If a patient is entering the study beyond the 30-day rollover window, changes to medical history and AEs that occur during that period will be collected.

10.1.2 Vital Signs

Vital signs will include diastolic blood pressure (DBP) and systolic blood pressure (SBP) as well as heart rate.

The patient should sit quietly for 5 minutes prior to collection of vital signs. At all time points, vitals will be collected prior to blood collection. Blood pressure (BP) and heart rate will be measured using a calibrated, fully automated machine with a cuff that is appropriate to the size of the upper arm. If a fully automated machine is not available, BP may be measured manually. The same method (either automated or manual) and the same arm (right or left) must be used throughout the study. The patient should be in a seated position with feet touching the floor. Patients should be seated quietly for at least 5 minutes in a chair with their backs supported, their feet flat on the ground, and their arms bared and supported at heart level.

10.1.2. Weight and Body Mass Index

Weight will be measured on a calibrated scale while fasted and after voiding. Body weight will be measured while fasting, using consistent scales, after voiding, and without shoes and outerwear (eg, coats).

Body mass index (BMI) will be calculated using the formula:

BMI $(kg/m^2) =$ weight in kg / (height in meters)²

10.1.3. Physical Examination

Physical exam (PE) will include an assessment of the following:

- General appearance
- Skin
- Eyes, ears, nose, and throat
- Head and neck
- Extremities
- Musculoskeletal examination
- Respiratory examination
- Cardiovascular assessment, including rhythm and presence of cardiac abnormalities
- Abdominal examination
- Neurologic examination including documentation of the presence of abnormalities in mental status and motor and sensory function
- Any additional assessments deemed necessary by the investigator

Documentation of the PE findings will be included in the source documentation at the clinical site. Only changes from baseline PE findings that meet the definition of an AE will be recorded on the AE page of the eCRF.

Note: Additional information will be collected regarding muscle-related AEs. See Section 12.6.

10.1.4. Clinical Laboratory Tests

10.1.4.1. Laboratory Parameters (Safety)

Patients will be in a seated position during the blood collection. Clinical laboratory parameters and tests will include those listed in Table 3. Collection schedule, schedule of laboratory parameters by visit, and instructions are in the Clinical Laboratory Manual provided by Central Laboratory.

| Clinical Laboratory Test | Clinical Laboratory Test | | |
|--|---|--|--|
| • Hematology | Blood Chemistry (serum, fasting)• Albumin (Alb)• Alkaline phosphatase (ALK-P)• Alanine aminotransferase (ALT; SGPT)• Aspartate aminotransferase (AST; SGOT)• Blood urea nitrogen (BUN)• Calcium (Ca) | | |
| Hematocrit (Hct) Hemoglobin (Hgb) Mean corpuscular hemoglobin (MCH) Mean corpuscular hemoglobin concentration (MCHC) Mean corpuscular volume (MCV) Platelet count | | | |
| Red blood (RBC) cell count White blood (WBC) cell count with differential (absolute and %) | Carbon dioxide (CO₂) Chloride (Cl) Creatinine Creatine kinase (CK) | | |
| Urinalysis (Dipstick) Clarity Bilirubin Color Glucose Ketones Leukocyte esterase Nitrate Occult blood pH Protein Specific gravity Urobilinogen | Glucose Lactate dehydrogenase (LDH) Phosphorus Potassium (K) Sodium (Na) Total and direct bilirubin (TB)^a Total protein Uric acid Coagulation—only in patients receiving anticoagulant therapy that in the investigator's judgment require monitoring at Month 0 and 3 to 5 days post-Month 0 Prothrombin time (PT) International normalized ration (INR) | | |
| Urinalysis (Microscopic)-only if urine dipstick abnormal Bacteria Casts Crystals Epithelial cells RBC WBC | Other Labs: • Urine pregnancy test • Hemoglobin A _{1C} (HbA _{1C}) | | |

Table 3: **Clinical Laboratory Parameters (Safety)**

10.1.4.2. Sample Collection, Storage, and Shipping

Clinical laboratory samples will be collected by appropriate clinical site personnel and then shipped according to a separate laboratory manual provided by the Central Laboratory. Samples will be processed by the Central Laboratory.

Blood draws for lipids, TG, and glucose must meet the criteria listed below. If these criteria have not been met, these blood samples will NOT be collected. If these criteria can be met by rescheduling the clinic visit to occur within 3 days, the lipid, TG, and/or glucose blood samples will be collected at the rescheduled clinic visit only.

• Blood samples will be drawn after a minimum 10-hour fast (water is allowed)

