9.2.4. Month 12 (Week 52 ±7 days)

If the patient is withdrawing early from the study at this visit, proceed to Section 9.3.2 for the list of the required assessments.

If the patient is withdrawing from IMP treatment at this visit, proceed to Section 9.3.2 for the list of the required assessments. The patient will be asked to continue to be followed for safety using the protocol-specified visit schedule. If the patient consents for follow-up, schedule the next protocol-specified visit.

Patients who do not provide consent to continue to return to the clinic for safety assessments after withdrawing from IMP treatment will be asked to participate in phone calls from the site at protocol-specified visits, or at a minimum at 78 weeks, to inquire about the patient's current health status and collect information on AEs (eg, recent procedures, hospitalizations, and if the patient has died, the cause of death). If the patient consents for telephone contacts, schedule the next protocol-specified visit.

Patients will undergo the following assessments and procedures:

- Concomitant medication review (ongoing)
- Assess AEs, SAEs, and potential clinical endpoints
- Weight
- Vital signs
- Physical Exam
- Clinical laboratory evaluations:
 - Hematology, blood chemistry, and urinalysis
 - Basic fasting lipids (TC, calculated LDL C, HDL C, non-HDL C, and TG)
 - ApoB and hs-CRP
 - HbA_{1C}
- Return of IMP; assessment and recording of IMP compliance
- Dispense IMP containers to patient for continued dosing and provide dosing instruction
- Schedule next visit

Note: If this visit is being conducted at the site for patients who have consented to be followed for safety assessments, including basic fasting lipids, after withdrawing from IMP treatment, all assessments except for those procedures pertaining to IMP management (IMP dispensing, IMP compliance, IMP accountability) should be completed.

Note: If this visit is being conducted by telephone contact for patients who have consented to be followed by phone for safety assessments after withdrawing from IMP treatment, collect information as reported by the patient regarding AEs, concomitant medication, and current health status.

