9.2.6. Treatment Month 18/EOT (Week 78 ±7days)

Patients will undergo the following assessments and procedures when completing the End of Treatment (EOT) visit, withdrawing from study prior to Week 78 (early withdrawal), or withdrawing from IMP treatment:

- Concomitant medication review (ongoing)
- Assess AEs, SAEs, and potential clinical endpoints
- Weight
- Vital signs
- Physical exam
- Clinical laboratory evaluations:
 - Hematology, blood chemistry, and urinalysis
 - Basic fasting lipids (TC, calculated LDL C, HDL C, non-HDL C, and TG)
 - ApoB and hs-CRP
 - HbA_{1C}
- Return of IMP; assessment and recording of IMP compliance
- Complete study status in IWRS (ie, early withdrawal or completed study).

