11.6.2. Clinical Laboratory Tests (Lipids)

Clinical laboratory samples will be collected at all clinic visits. All efforts should be made to collect these samples within the visit window.

Patients are encouraged to be in a seated position during the blood collection. Clinical laboratory parameters and tests will include those listed in Table 4. Collection schedule and instructions are provided in the Clinical Laboratory Manual. A description of the sample collection, storage, and shipping as well as monitoring and management of abnormal laboratories are described in Section 10.1.4.

When vital signs and laboratory samples are to be collected at the same time point, vital sign measurements will precede laboratory sample collection.

| Table 4: | Clinical Laboratory Parameters (Lipids) and Cardiometabolic Biomarkers |
|----------|--|
| | |

| Clinical Laboratory Test | Clinical Laboratory Test |
|---|--|
| Basic Lipid Parameters | Other Parameters |
| • Total cholesterol (TC) | • High-sensitivity C-reactive protein (hs-CRP) |
| • low-density lipoprotein cholesterol (LDL-C) and non-HDL-C | • ApoB |
| • High-density lipoprotein cholesterol (HDL-C) | |
| • Triglycerides (TG) | |

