## 5.3 Efficacy Endpoints and Analyses

Given the primary objective of the study being long term safety, efficacy analyses will be using the safety population (SP). The efficacy data will be summarized by previous treatment group in parent study as well as an overall group.

For each efficacy parameter, descriptive summary statistics at each visit will be provided for the observed value, change from baseline, and percent change from baseline in both conventional and International System of Units (SI). Two sets of summaries will be provided using the baseline from the parent study and from the OLE study. The visits to be included in the overtime summary are baseline of parent study (1002-040), baseline of OLE study, week 12, week 52, week 78, and Week 82. There will be no imputation for missing data, all summaries will use the observed data. Ninety-five percent (95%) CI will be provided for the estimates at post-baseline visits.

In addition, efficacy parameters will also be summarized using the Completer Analysis Set (CAS).

For LDL-C, the same descriptive summary statistics at each scheduled visit will be provided within each subgroup for the observed value, change from baseline, and percent change from baseline.

Efficacy data (observed value, change from baseline, and percent change from baseline) from all visits will be summarized using descriptive statistics in both conventional and standard units.

Figures (mean  $\pm$  standard deviation or median/interquartile range) supporting the summary tables will be provided for each efficacy parameter.

Efficacy data from all visits will be provided in listings as well.

By-visit summary for efficacy endpoints (LDL-C, non-HDL-C, TC, HDL-C, TG, ApoB, and hs-CRP,) using the CAS will be provided in conventional and standard units.

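### The 3-day limit on a fasted redraw in Protocol 10.1.4.2 is shorter than most of the ±7-day visit window, so some obtainable Week 52 and Week 78 lipid values may go uncollected

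*Protocol*

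**What the plan says.** Protocol Section 10.1.4.2 requires a fast of at least 10 hours before blood is drawn for lipids, TG and glucose. For a patient who arrives without it, the rule is "If these criteria have not been met, these blood samples will NOT be collected". The exception begins "If these criteria can be met by rescheduling the clinic visit to occur within 3 days, the lipid, TG, and/or glucose blood samples", and those samples are then taken at the rescheduled visit only. The section does not mention a fasted draw later than 3 days.

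Protocol Sections 9.2.4 and 9.2.6 and the schedule in Appendix 1 give the Week 52 and Week 78 visits a window of ±7 days. On lipid samples, Section 11.6.2 says: "All efforts should be made to collect these samples within the visit window". The same section refers the reader to Section 10.1.4 for how samples are collected.

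SAP v1.3, Section 5.1, assigns samples from Days 309 to 406 to Week 52 and from Days 498 to 562 to Week 78. On missing values, SAP Section 5.3 states: "There will be no imputation for missing data, all summaries will use the observed data". Protocol Section 12.5 also plans no imputation.

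**The concern.** The fasting rule protects the quality of the sample. The 3-day limit is a separate restriction, and the documents give no analytic reason for it. An unfasted patient who could come back fasted on day 5 or 6, still inside the visit window, has no stated route to a lipid sample. Non-collection is the default, so a careful site would not draw one.

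No other scheduled visit replaces the lost value. Weeks 36 and 64 are telephone visits without laboratory tests, and Week 82 is off study drug with its own analysis window. Because summaries use observed data only, the patient drops out of that visit's results for all five basic lipid parameters, at one of only two endpoint visits. The stake is avoidable missing data in the secondary efficacy summaries.

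**Working it through.** The plan states no figure on this point, so there is none to reproduce. The check is a count of days, followed by an illustration on assumed rates.

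**Inputs from the documents.** Redraw limit 3 days (Protocol 10.1.4.2). Visit window ±7 days (9.2.4, 9.2.6). Analysis windows Days 309–406 and 498–562 (SAP v1.3, 5.1). Planned enrolment about 1300 (Protocol 6.5). Target days are 52 × 7 = 364 and 78 × 7 = 546, so the visit windows are Days 357–371 and 539–553.

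**Step 1: redraw limit against visit window.** Let d be the day of the unfasted visit relative to target, from −7 to +7.

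- Days left in the visit window: 7 − d
- In-window days given up under the 3-day limit: max(0, 4 − d)
- Days by which the limit runs past the window: max(0, d − 4)

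| d | Days left in window | In-window days given up | Days past window |
|---|---|---|---|
| −7 | 14 | 11 | 0 |
| 0 | 7 | 4 | 0 |
| +3 | 4 | 1 | 0 |
| +4 | 3 | 0 | 0 |
| +5 | 2 | 0 | 1 |
| +7 | 0 | 0 | 3 |

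The limit is the shorter of the two for d = −7 to +3, which is 11 of 15 days. The two coincide at +4. At +5 to +7 the 3-day limit is the more generous. With the 15 days weighted equally (an assumption), the in-window days given up are (11 + 10 + … + 1)/15 = 66/15 = 4.4 on average.

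**Step 2: would a later draw be analysed?** Yes. The visit windows end on Days 371 and 553, inside the analysis limits of 406 and 562. The latest draw that either rule could give, target + 7 + 3, is Day 374 or Day 556, also inside.

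**Step 3: endpoints affected.** The rule names lipids, TG and glucose. Protocol 9.2.4, 9.2.6 and Appendix 1 list ApoB and hs-CRP apart from the basic fasting lipids, and Table 4 puts them under other parameters. The parameters clearly affected are LDL-C, non-HDL-C, TC, TG and HDL-C, 5 of 7. LDL-C carries two endpoints, so this is 6 of the 8 secondary endpoints.

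**Step 4: illustrative size.** The documents give neither the share arriving unfasted nor the share of those who could return only after day 3 but inside the window. Assume 2% to 10% for the first and 10% to 50% for the second.

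- Values lost per visit: 1300 × 0.02 × 0.10 = 2.6, up to 1300 × 0.10 × 0.50 = 65. The lost share f is 0.2% to 5%.
- Widening of a 95% CI: 1/√(1 − f) = 1.001 to 1.026.
- Shift in the observed mean if lost patients differ from observed ones by 10 points in LDL-C percent change: f × 10 = 0.02 to 0.5 points.

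**The case against.** The strongest reply is that a site can follow both sections. Section 11.6.2 asks for effort to sample within the window, does not promise a redraw on every day of it, and defers to Section 10.1.4 for collection. That stands. A reader might infer that the two sections give opposite instructions, but the text does not support this. They differ in reach and should be aligned.

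Second, only patients who arrive unfasted are touched, and no existing sample is thrown away. That also stands. A reader might say that values are discarded or that a later draw is forbidden. In fact the sample is not drawn, and collection after day 3 is left unaddressed, with non-collection the natural reading. The laboratory manual, which is not among the documents, may say more.

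Third, Section 9.3.2 offers flexibility: "Accommodations for early or late visits in special circumstances will be considered by the Sponsor to prevent early withdrawal". This helps little. It is discretionary, meant for special circumstances and aimed at preventing withdrawal, so it is not a routine route for an unfasted patient who stays in the study.

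Fourth, a short limit keeps the lipid draw close to the other assessments of the visit. That may be the motive, but the documents do not say so, and the SAP's much wider analysis windows show no need for it.

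Last, the consequence is small. The primary endpoint is AE incidence, the analyses are descriptive, and Protocol 12.1 plans no inference. That is correct and sets the weight of the point.

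**Conclusion.** The point holds as a minor one. As written, the rule can leave uncollected some fasted lipid values that could be obtained in the visit window and would be analysed. It changes no error rate, sample size or primary result.

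The day counts follow from the documents. The loss of 0.2% to 5% and the shift of 0.02 to 0.5 points rest wholly on the assumed shares and the assumed 10-point difference. The average of 4.4 days counts calendar days; it is not a probability of losing a value.

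A reader might infer that the missing patients are mainly the less adherent ones, so that the long-term effect looks better than it is. The documents do not show who arrives unfasted or why a patient cannot return within 3 days. Missing one fast is not poor tablet adherence, and work or travel can explain a late return. The direction of any shift is unknown. Nor should the loss be extended to ApoB and hs-CRP: Section 7.1 asks for fasting before all laboratory samples, but the non-collection rule does not name these two.

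**What to change.** In Protocol Section 10.1.4.2, replace the 3-day limit with: *within the visit window for that visit or within 3 days, whichever is later*. Apply this to the samples the rule already names, and keep the 10-hour fast. Do not add ApoB or hs-CRP to the sentence, since that could extend non-collection to two endpoints it does not now cover. Bring the laboratory manual into line.

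The words *whichever is later* matter. Allowing the redraw only to the end of the visit window would cut the redraw days for visits at +5, +6 and +7 from 3 to 2, 1 and 0. The average gain would then be (105 − 45)/15 = 4.0 days. With *whichever is later*, no visit loses redraw time. The available days total 102 for offsets −7 to +4 plus 9 for +5 to +7, and the gain is (111 − 45)/15 = 4.4 days.

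The cost is one protocol sentence and a laboratory-manual note. No visit or procedure is added beyond the rescheduling already allowed. The small downside is that some visits fall later in their existing window. This is a cheap improvement.

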10.1.4.3. General Monitoring and Management of Abnormal Clinical Labs

It is the Investigator's responsibility to review the results of all laboratory tests as they become available and to sign and date the report to document their review. For each laboratory test outside of the laboratory normal range, the Investigator needs to ascertain if this is a clinically significant change from baseline for the individual patient, with baseline defined as the last value or observation before the first dose of study drug. The Investigator may repeat the laboratory test or request additional tests to verify the results of the original laboratory test.

If a laboratory value is determined to be an abnormal and clinically significant change from baseline for the patient, the Investigator should determine if it qualifies as an AE, and if yes, an appropriate eCRF will be completed. All clinically significant laboratory abnormalities occurring during the study that were not present at baseline should be followed and evaluated with additional tests if necessary, until diagnosis of the underlying cause or resolution. Specific monitoring and management guidelines for laboratories of special interest are outlined in the sections below.

10.1.4.3.1. Monitoring and Management of Elevated Liver Function Tests

If at any time after randomization a patient experiences a new alanine aminotransferase (ALT) and/or aspartate aminotransferase (AST) $>3 \times$ the upper limit of normal (ULN), the patient will undergo repeat confirmatory liver function test (LFT) assessment as soon as is reasonably possible, preferably within 3 to 7 days of the laboratory result becoming available.

Repeat LFT assessment will include: 1) measurement of ALT, AST, alkaline phosphatase (ALK-P), total and direct bilirubin, prothrombin time (PT)/international normalized ratio (INR), eosinophil count, creatine kinase (CK), antihepatitis A virus (total), hepatitis B surface antigen (HBsAg) (confirmation of screening measurement), hepatitis C virus (HCV) (confirmation of screening measurement), and anti-cytomegalovirus/immunoglobulin M; 2) history of concomitant medication use; 3) history of exposure to environmental chemical agents, including ethanol; and 4) query for related symptoms. Additionally, further testing such as liver ultrasound or magnetic resonance imaging (MRI) scanning may be warranted to rule out additional pathology depending on clinical presentation and should be discussed with the Sponsor personnel or the authorized Medical Monitor.

• If repeat LFT assessment confirms ALT and/or AST $>3 \times$ ULN, consideration should be given to withdrawing the patient and administering no further doses of study drug.

At the investigator's discretion, study drug may be interrupted and the patient rechallenged with study drug after LFTs have returned to baseline levels.

- If repeat LFT assessment confirms ALT and/or AST >5 × ULN, patient should be withdrawn from IMP treatment, but will be asked to continue to be followed for safety using the protocol-specified visit schedule (see Appendix 1).
- If repeat LFT assessment confirms ALT and/or AST >3 × ULN in addition to any of the following, the patient should be given no further IMP treatment, but will be asked to continue to be followed for safety using the protocol-specified visit schedule (see Appendix 1):
 - TB > $2 \times ULN$

Note: In the case of patients with Gilbert's disease, total bilirubin (TB) will be fractionated and the determination of $2 \times ULN$ will be based upon direct (conjugated) bilirubin.

- INR >1.5 × ULN (unless the patient is on stable dose of anticoagulation medication)
- Appearance or worsening of right upper abdominal discomfort, anorexia, fatigue, nausea, vomiting, fever, rash, or eosinophilia

